3.4 Analysis of Efficacy Endpoints

3.4.1 Calculation Examples for Daily Measures

Below are examples of how the eDiary and actigraphy endpoints will be calculated based upon windows outlined in [Table 4](#) and rules outlined in [Section 2.4](#).

1. Example 1 (complete data)
 - a. The subject has results for all seven days leading up to the visit (e.g. $x_8, x_9, x_{10}, x_{11}, x_{12}, x_{13}, x_{14}$).
 - b. The average for Week 2 is $(x_8 + x_9 + x_{10} + x_{11} + x_{12} + x_{13} + x_{14})/7$.
2. Example 2 (incomplete data, completed in the extended range)
 - a. The subject has results for less than seven days in the original range (e.g. $x_{22}, x_{24}, x_{25}, x_{27}, x_{28}$) but have enough in the extended range to reach seven results overall (e.g. x_{29}, x_{31}). In this example the subject is missing diary data on days 23, 26, and 30.
 - b. The average for Week 4 is $(x_{22} + x_{24} + x_{25} + x_{27} + x_{28} + x_{29} + x_{31})/7$.

3. Example 3 (incomplete data)

- a. The subject has results for less than seven days in the original range (e.g. x_{40}, x_{42}) and does not have enough in the extended range to reach seven results overall (e.g. x_{44}, x_{48}, x_{49}). In this example the subject is missing diary data on days 36, 37, 38, 39, 41, 43, 45, 46, 47 and 49.
 - The average for Week 6 is $(x_{40} + x_{42} + x_{44} + x_{48} + x_{49})/5$.

4. Example 4 (confounding event)

- a. The subject has results for all seven days leading up to the visit but has a confounding event part way through window (e.g. $x_8, x_9, x_{10}, x_{11}, x_{12}, x_{13}, x_{14}$ all exist but excluded medication or therapy was received on day 11).
- b. The average for Week 2 is $(x_8 + x_9 + x_{10})/3$.

5. Example 5 (no data)

- a. The subject does not complete the diary after day 10 or had a confounding event before day 10.
- b. The average for Weeks 4 and 6 are missing.

3.4.2 **WI-NRS**

The WI-NRS endpoints (result, change from baseline, percent change from baseline, 3-point and 4-point responders) will be summarized at the primary time point, Week 6, as well as at Week 2, 4 and Follow-up. The summary measures will include 95% Wald confidence intervals for the treatment difference. The baseline WI-NRS will also be summarized, though no confidence interval will be produced. A graph of the mean WI-NRS results and change from baseline results by timepoint and treatment will be produced as well as a cumulative distribution function plot (CDF plot) of the Week 6 results.

The WI-NRS scores for days -7 to 14 will be plotted by averaging the available data across subjects within treatment group and study day. These results will be summarized in a table along with change from baseline where baseline is defined in the identical manner used for the weekly measures, see [Table 4](#).

The summary measures for the WI-NRS change from baseline results and the 4-point responder rate will be produced using four endpoint derivation methods, one primary method and three sensitivity measures. The difference between these methods is how the weekly measures are calculated. The primary derivation method uses all reported data prior to use of excluded therapy or changes to allowed adjunctive therapies and the missing data imputation rules outlined in [Section 2.7](#). Sensitivity analyses as defined in [Section 2.8](#) will also be conducted.

Testing will be used for the change from baseline and 4-point responder rates endpoints at Week 6. The test used for the 4-point responder rate (primary endpoint) is a CMH test controlling for the 'as randomized' stratification factors. The 'as randomized' stratification factors are based upon the stratification cell the subject was randomized to. The differences

between treatment groups for the change from baseline measure will be tested using an ANOVA model controlling for the stratification factors. A main effects model with an interaction term (treatment by stratification factors) and a Type II hypothesis will be used. Each serlopitant treatment group (1 mg and 5 mg) will be compared to placebo separately and the multiplicity rules outlined in [Section 1.6](#) will be used to interpret these p-values.

‘Sensitivity’ p-values will be constructed using multiple imputation (MI) methodology. This approach imputes randomly generated values instead of the fixed value. Using the example from [Section 2.6](#) (i.e. a subject had data up to Week 4 but is missing their Week 6 results: $\Delta_4 + \Delta_{(4,6)}$), at least 1,000 random realizations of $\Delta_{(4,6)}$ will be generated using code similar to the following,

```
proc mi nimpute=1000;  
class trt;  
monotone reg(x);  
var trt x;
```

From these realizations of $\Delta_{(4,6)}$ the change from baseline to Week 6 will be calculated. Hence, there will be at least 1,000 random realizations of the responder status. The p-value from the MI analysis will be calculated using the SAS software procedure `mianalyze`.

Finally, the change in WI-NRS results will be summarized within the subgroups outlined in [Section 2.8](#). Forest plots based upon the same subgroups will also be produced.

3.4.3 *ItchyQol*

The ItchyQol endpoint will be summarized at Baseline, Week 2, 4, 6 and Follow-up. The summary measures will include 95% Wald confidence intervals of the treatment difference. In addition, a graph of the mean score by treatment and timepoint will be produced along with a graph of change from baseline. The difference between serlopitant 1 mg and 5 mg individual versus placebo at Week 6 will be tested with the identical ANOVA model as used for the change from baseline WI-NRS endpoint.

3.4.4 *Additional and Exploratory Endpoints*

The additional and exploratory endpoints (AI-NRS, sPGA, IGA-AD, 5-D Pruritus Scale, Actigraphy endpoints) will be summarized at baseline, Week 2, 4, 6 and Follow-up. The result as well as change from baseline will be summarized. The PGIC endpoint is a change measure so only the results at each time point will be summarized. As the 5-D Pruritus Scale was introduced into the study part way through the study, only subjects with a baseline value will be included in the summary table.

For the IGA-AD endpoint a separate analysis will be performed where the result is dichotomized to responder/non-responder. This measure will be summarized at Week 2, 4, 6 and Follow-up and be limited to subjects with a mild or greater assessment at baseline.

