1.6 Decision Rule and Sample Size

The significance level for this study is 5% (one-sided). If the one-sided p-values are less than 5% then the null hypothesis of no treatment effect is rejected. If the one-sided p-values are additionally less than 2.5%, then the serlopitant-based regimen will have met the generally accepted level of evidence required to demonstrate efficacy.

This study contains two active dosing arms. A stepdown procedure will be used to control for multiplicity. This procedure will start by testing the primary endpoint for the 5 mg treatment group and then proceed to the 1 mg group should statistical significance (one-sided p-values < 0.05) be reached for the 5 mg vs placebo comparison.

Statistical significance for the key secondary endpoints will be dependent upon statistical significance being reached for the primary endpoint at the given dose level (i.e. a gatekeeper within dose arm will be used for the secondary endpoints). As there are multiple secondary endpoints a stepdown procedure will be used starting with the WI-NRS 4 point responder rate endpoint, then the ItchyQoL.

The target sample size of 450 randomized and dosed subjects (150 per group) has been determined based upon a 1:1:1 allocation of subjects to treatment groups, an assumed common treatment effect for the 1 mg and 5 mg arms, and a 5% one-sided alpha level. One-hundred and fifty subjects per group results in 90% power for each test individually assuming a treatment effect (placebo change from baseline - serlopitant change from baseline) of -1 and a standard deviation of 2.9.

The sample size calculations have been performed in PASS 13 using a t-test. The primary analysis will control for the stratification factors. It is expected that this unstratified power estimate will under-estimate the true power as it does not take the variance reduction resulting from stratification into account ([Matts and Lachin 1988](#)).

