The Itch NRS is an instrument for measurement of itch intensity that asks subjects to rate the intensity of their itch on an 11-point scale ranging from 0 (no itch) to 10 (worst itch imaginable) during a 24-hour recall period. Both WI-NRS and AI-NRS during a 24-hour recall period will be captured. The daily NRS results will be summarized at Weeks 2, 4, 6 and follow-up as outlined in [Section 2.4](#). A 4-point responder is a subject who had at least a 4-point reduction in score between the visit and baseline. A 3-point responder is similarly defined.

2.3.3 *Static Patient Global Assessment of Itch Severity*

The sPGA assesses overall itch severity by asking the severity of itchiness in the past 7 days on a 5-point scale as none (0), mild (1), moderate (2), severe (3), and very severe (4).

2.3.4 *Patient Global Impression of Change in Itch Severity*

The PGIC in Itch Severity is a single item measure that assesses the change in overall itch severity since the Baseline visit on a 7-point scale from (very much better) to (very much worse).

2.3.5 *ItchyQoL*

ItchyQoL is a 22-item pruritus-specific instrument that measures the degree to which pruritus affects quality-of-life. The responses to the items are Never (1), Rarely (2), Sometimes (3), Often (4) and All the Time (5). This impact is quantified into 3 subscales (symptom, function, emotion) and an overall score. A higher score corresponds to a more adverse impact. The overall score is the average of the 22 items. If an item is missing the total score will be missing. The score for each subscale is the average score for the items that make up the subscale. The items that make up the subscales are,

- Symptom subscale score (items 1-6):
 - My itchy skin condition bleeds,
 - My skin hurts because of my itchy skin condition,
 - My itchy skin condition burns or stings,
 - I get scars from my itchy skin condition,

- I need to scratch my itchy skin condition,
- Temperature/seasonal changes aggravate my itchy skin condition
- Function subscale score (items 7-13):
 - I spend a lot of money treating my itchy skin condition,
 - My itchy skin condition makes it hard to work or do what I enjoy,
 - My itchy skin condition affects my interaction with others,
 - My itchy skin condition affects how well I sleep,
 - My itchy skin often makes it difficult to concentrate,
 - My itchy skin condition limits the types of clothes I can wear,
 - My itchy skin condition forces me to buy special soaps, detergents, and lotions.

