2.8 Sensitivity Analyses, Subgroups and Covariates

Descriptive statistics for the change in WI-NRS at Week 6 will be provided for the subgroups indicated below. Forest plots of the difference and confidence interval for this difference will also be created. The subgroups include,

- Sex
- Age Group (< 18 years, 18 to 64 years, > 64 years)
- Race
 - All race groups with less than 30 subjects will be combined with 'Other'
 - A White versus Non-White comparison will be made
- Baseline WI-NRS
- Baseline IGA-AD
- Use of allowed concomitant medications as outlined in Section 5.7.1 of the protocol
- Treatment completion (completed treatment, did not complete treatment).

To investigate the impact of missing data / confounding sensitivity analyses will be performed for the WI-NRS endpoint. These methods include,

1. Multiple imputation, MI, methods will be used to recalculate the p-values at Week 6.
2. The summary statistics will be produced where the missing data is imputed using
 - a. Data after the confounding event are excluded with no imputation

- b. Last Observation Carried Forward (LOCF),
- c. Baseline Observation Carried Forward (BOCF).

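### The multiple-imputation check in SAP 3.4.2 draws the Week 4 to 6 itch step from treatment arm alone, so it cannot test the primary rule's assumption that the step is unrelated to the current score

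*SAP*

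**What the plan says.** **Primary rule.** SAP 2.7 (and Protocol 8.2) imputes a missing Week 6 WI-NRS change as the subject's last observed change plus the mean later step of the subject's own arm, as a fixed value.

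**Sensitivity rule.** SAP 2.8 states: "Multiple imputation, MI, methods will be used to recalculate the p-values at Week 6". The other methods listed there (no imputation, LOCF, BOCF) give summary statistics. SAP 3.4.2 describes the multiple imputation as replacing the fixed step by at least 1,000 random ones. In the sample PROC MI call, treatment is the only variable ahead of the imputed x, and no minimum or maximum is set. Then "From these realizations of $\Delta_{(4,6)}$ the change from baseline to Week 6 will be calculated", and responder status follows from the same draws. The code is offered as similar to what will be run. The symbol x is not defined, but the text implies that it is the Week 4 to 6 step.

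**Scale and entry.** SAP 2.3.2 describes an "11-point scale ranging from 0 (no itch) to 10 (worst itch imaginable"). Protocol 4.2, criterion 4, requires a weekly mean of at least 6 in each screening week.

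**Why data go missing.** SAP 2.6 drops WI-NRS values from the day of a confounding event. Protocol 5.7.3 stops study drug when excluded therapy is used for dermatitis or itch. Protocol 8.8 discusses withdrawal for lack of efficacy.

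**The concern.** Weekly itch means are noisy and bounded. Subjects with a high score at Week 4 tend to come down, and subjects near zero cannot fall much further. The step from Week 4 to Week 6 should therefore depend on the Week 4 score. Both the primary rule and the multiple imputation assume that it does not.

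A sensitivity analysis is most useful when it relaxes the doubtful assumption of the primary analysis. This one keeps that assumption and changes only the variance, yet it is the only sensitivity method that yields a p-value. If serlopitant works, more placebo subjects may reach for excluded therapy or leave because of poor control. Those subjects would keep their poor Week 4 result with no return toward the mean, which makes placebo look worse than it is.

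**Working it through.** **1. The plan's own figure.** SAP 1.6 gives: "The significance level for this study is 5% (one-sided"); "One-hundred and fifty subjects per group results in 90% power for each test individually"; effect "of -1 and a standard deviation of 2.9".

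- SE = 2.9 × √(2/150) = 0.335.
- 1/0.335 − 1.645 = 1.34, so power is 91.0% (noncentral t: 90.9%). The stated 90% is reproduced.

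The plan gives no figure for the multiple imputation. The SE of 0.335 serves as a yardstick below.

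**2. Formula for the bias.** Let d4 and d6 be a subject's changes from baseline at Weeks 4 and 6. Within an arm, suppose d6 = a + b·d4 + error, with missingness depending only on d4.

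- Mean step among observed subjects: a − (1 − b)·(mean d4, observed).
- The plan's mean for missing subjects: (mean d4, missing) + a − (1 − b)·(mean d4, observed).
- Their true mean: a + b·(mean d4, missing).
- The difference, weighted by the missing fraction m, is: **arm bias = m × (1 − b) × (mean d4 missing − mean d4 observed)**.

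The bias of the treatment difference is the active arm's bias minus the placebo arm's. It is zero if b = 1, if missingness is unrelated to d4, or if the two arm biases are equal.

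**3. Assumptions.** The documents give no drop-out rate, no Week 4 to 6 correlation and no Week 4 SD. Assumed: SD 2.9 at both weeks, so b equals the correlation; correlation 0.6, 0.8 or 0.9; missing fraction 10 to 30%; logistic drop-out on d4. The effect is serlopitant minus placebo, true value −1, so negative bias favours serlopitant. The simulation used 2,000,000 subjects per arm.

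**4. Results (bias of the treatment difference).**

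| Missingness | Corr. 0.6 | 0.8 | 0.9 |
|---|---|---|---|
| Unrelated to response | 0 | 0 | 0 |
| 15% in both arms, same dependence on response | 0.002 | −0.001 | −0.001 |
| One drop-out model, placebo 15%, active 12% | −0.03 | −0.02 | −0.01 |
| Poor responders leave, placebo 20%, active 10% | −0.11 | −0.05 | −0.03 |
| Poor responders leave, placebo 30%, active 10% | −0.21 | −0.11 | −0.05 |

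Check against the formula at correlation 0.9, 20% versus 10%. The arm biases were 0.056 (placebo) and 0.030 (active), so the difference is 0.030 − 0.056 = −0.026. They imply gaps in d4 of 0.056/(0.20 × 0.10) = 2.8 and 0.030/(0.10 × 0.10) = 3.0 points.

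With the Week 4 change as a covariate within arm, the bias was 0.002 or less in every scenario. Against the yardstick, 0.21/0.335 is about 0.6 of a standard error and 0.03/0.335 about 0.1.

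**5. A trial-sized check.** This used 150 per arm, about 15% missing, scores clipped to 0–10, and correlations 0.7, 0.8 and 0.9.

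- Poor responders leaving on placebo only: the plan's model overstates a true difference of about 0.88–0.90 by 0.10, 0.06 and 0.03. Conditioning on Week 4 change and baseline is within 0.002.
- Same mechanism in both arms: SE 0.333, 0.324 and 0.313 under the plan, against 0.318, 0.314 and 0.308 with conditioning. The ratios are 1.047, 1.032 and 1.016.

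**6. Values off the scale.** At correlation 0.8 the step SD is 2.9 × √(2 × 0.2) = 1.83. Assume a mean step of −0.5.

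- Week 4 score 1: P(N(0.5, 1.83) < 0) = 39%.
- Week 4 score 9: P(N(8.5, 1.83) > 10) = 21%.

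In simulations bounded to 0–10, about 4 to 26% of draws left the scale. The fixed primary rule also left it, in about 0.1 to 20% of imputed values.

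Effect on responders: with baseline at least 6, a draw below 0 is a fall of more than 6, and a score of 0 is a fall of at least 6; both count as response. A draw above 10 is a rise from baseline, and a score of 10 cannot be a fall; neither counts. Four-point responder status does not change.

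**The case against.** The strongest reply is that the documents promise no more than this. Protocol 8.2 announces a similar approach with a multiple-imputation step, and SAP 3.4.2 says that random values replace the fixed one. Keeping the step and adding randomness delivers that. The code is labelled illustrative, so a better model is already permitted. Multiple imputation has no part in the decision rule of SAP 1.6. The other sensitivity summaries come with 95% confidence intervals for the treatment difference, and neither BOCF nor no imputation uses the arm-average step. All of this stands, and it limits the consequence. It does not answer the point that the one check with a p-value shares the primary rule's main assumption. Better code is permitted, but it is not specified.

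Three stronger readings are tempting, and the documents do not support them.

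- A reader might infer that the Week 4 score is ignored. It is not: it enters as an offset with slope 1. What is left out is its relation to the step.
- A reader might infer that the treatment effect is biased whenever drop-out depends on earlier response. Such drop-out biases each arm's mean when b is below 1, but the difference is biased only when the arms differ in rate or dependence.
- A reader might infer that off-scale draws distort the 4-point responder rate. The entry criterion rules that out, as shown in the working.

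**Conclusion.** The point holds as a low-cost improvement. The multiple imputation adds variance to the primary rule and leaves untested its assumption that the step is unrelated to the current score.

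Where missing or confounded data differ between arms, the plausible bias is about 0.01 to 0.1 points on a planned difference of 1, reaching about 0.2 only with 30% versus 10% missing and a correlation of 0.6. In the scenarios where poor responders leave placebo more often, it favours serlopitant. With equal patterns there is no bias in the difference, only a standard error about 2 to 5% larger than a conditional model would give. The sizes depend on the assumed correlation, Week 4 SD and drop-out pattern; the direction depends on who drops out in which arm. Nothing here shows that the primary conclusion would change.

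**What to change.** In SAP 3.4.2, define x and replace the step model as follows.

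- Impute the Week 6 change, and the Week 4 change where it is missing, from treatment, as-randomized stratum, baseline WI-NRS and the earlier observed changes, using pre-confounding data only. Imputing Week 4 as well covers subjects last seen at Week 2, for whom the present text specifies no draw.
- Do not add the Week 2 change to a strictly monotone model without preparation: a subject with a Week 2 diary gap but a Week 4 mean breaks the monotone pattern. Either fill intermittent gaps first (for example, MCMC with the monotone option) or use fully conditional specification.
- Consider fitting by arm or adding treatment-by-stratum terms, because the analysis model contains that interaction.
- Derive the Week 6 change and responder status from the completed values.
- Optionally use predictive mean matching or bounded draws. Conditioning alone does not keep scores within 0–10: about 8 to 9% of draws were still off the scale, against 10 to 18% under the plan in the same run.

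The cost is a short SAP edit, a few more coefficients and slightly more programming. All variables are already collected, and no change to the protocol or data collection is needed.

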3.5 Analysis of Safety Endpoints

3.5.1 Adverse Events

AEs and SAEs will be recorded from the first study drug administration through the Follow-up visit. A treatment-emergent AE (TEAE) is an AE which started on or after the date of the first treatment. An overview of AEs, which includes subject incidence of TEAEs, treatment-related TEAEs, serious TEAEs, TEAEs by toxicity grade and TEAEs leading to permanent discontinuation of treatment. For TEAEs presented by toxicity grade, the worst grade during the clinical study will be presented for each subject.

The subject incidence of TEAEs, treatment-related TEAEs and TEAEs leading to permanent discontinuation of treatment will be summarized by system organ class and preferred term. Treatment-emergent AEs will also be summarized in a table by toxicity grade. For TEAEs presented by toxicity grade, the worst grade for each event during the clinical study will be presented for each subject.

All AEs will be presented as a listing by subject. A separate listing of pruritus and atopic dermatitis adverse events (as identified by the investigator) will be presented. TEAEs leading to treatment discontinuation will be provided in a separate listing.

SAEs will be listed and summarized in a similar manner to TEAEs.

3.5.2 Clinical Laboratory Evaluations

Summary statistics for actual values and for changes from baseline will be tabulated for clinical laboratory results by analysis window. Shifts from baseline clinical laboratory values based upon the normal range will be tabulated. These tables will utilize the normal ranges provided for the individual sample.

3.5.3 Vital Signs

The observed data at baseline and change from baseline for each measurement day will be summarized with descriptive statistics.

3.5.4 Electrocardiogram Results

The overall ECG assessment (abnormal or normal) will be summarized by treatment and analysis window. The QTcF values will be summarized by treatment and analysis window as both the QTcF value and change from baseline. A summary of the number of subjects with a value > 450, 480 and 500 and the numbers of subjects with change from baseline values > 30 and 60 by treatment and analysis window will be produced.

